5. Research involving materials (data, documents, records, or specimens) that have been collected, or will be collected solely for nonresearch purposes (such as medical treatment or diagnosis). (NOTE: Some research in this category may be exempt from the HHS regulations for the protection of human subjects. 45CFR 46.101(b)(4). This listing refers only to research that is not exempt.)

**Protocol Title:** Smoking Cessation Following Text Message Intervention in Pregnant Women

---

6. Collection of data from voice, video, digital, or image recordings made for research purposes.
7. Research on individual or group characteristics or behavior (including, but not limited to, research on perception, cognition, motivation, identity, language, communication, cultural beliefs or practices, and social behavior) or research employing survey, interview, oral history, focus group, program evaluation, human factors evaluation, or quality assurance methodologies. (NOTE: Some research in this category may be exempt from the HHS regulations for the protection of human subjects. 45 CFR 46.101(b)(2) and (b)(3). This listing refers only to research that is not exempt.)
- X 8. [FOR IRB use only]. Continuing review of research previously approved by a convened IRB only when condition (a), (b), or (c) is met.
- a) Previously approved research where
- (i) The research is permanently closed to the enrollment of new subjects;
- (ii) All subjects have completed all research-related interventions; and
- (iii) The research remains active only for the long term follow-up of subjects.
- b) Previously approved research where no subjects have been enrolled and no additional risks have been identified.
- X c) Previously approved research where the remaining research activities are limited to data analysis.
9. [FOR IRB use only]. Continuing review or research not conducted under an investigational new drug application or investigational drug exemption where expedited categories two (2) through eight (8) do not apply but the IRB has determined and documented at a convened meeting that the research involves no greater than minimal risk and no additional risks have been identified.

---

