Results of current studies looking at smoking cessation with the help of computer or other electronic device are mixed. Several trials have looked at the use of text-messaging based smoking cessation programs. One randomized controlled pilot trial of 151 daily smokers interested in quitting found a non-clinically significant difference in cessation rates at 3 months between the intervention and control groups (11% versus 4%), this study was not powered to detect a statistical difference. A small pilot study evaluating Text2Quit, an automated, personalized, and interactive program that sends texts and emails over the course of 3 months, reported liking the program at 2 and 4 weeks after enrollment (91% and 82%, respectively) and 75% of participants reported reading most or all of the messages sent. Unfortunately, the majority of participants admitted to smoking at the 4-week visit. The txt2stop study was a trial of 5800 smokers that were randomized to receive text messages that were comprised of motivational and behaviour-change support versus the control group who received text messages unrelated to quitting. At 6-months abstinence was significantly increased in the intervention group versus the control group (10.7% vs. 4.9%;  $p < 0.0001$ ).

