**If No, explain what SLU will NOT participate in:**

**Please save frequently**

Page numbers from a sponsor's protocol/grant may be referenced in 3b, 3c, and 3d.

- b) **Describe all the procedures, from screening through end-of-study, that the human subject must undergo in the research project, including study visits, drug treatments, randomization and the procedures that are part of standard of care. Specify which procedures are for research and which are standard of care. Please note: The box below is for text only. If you would like to add tables, charts, etc., attach those files in the Attachment section (#16).**

This is a randomized, open-label, prospective trial that will evaluate the impact of texting to pregnant, underserved, cigarette smokers on smoking cessation rates. It will be conducted over 18-months, with subject recruitment over 12 months, at St. Mary's Health Center Maternal Fetal Care Center. Potential patients will be identified through EPIC chart review as well as from referrals from providers. These patients will be screened for inclusion and exclusion criteria through a chart review as well as meeting with pharmacy to determine the patient's stage of change and willingness to set a quit date within the next 30 days. Informed consent will be obtained if the patient is eligible and willing to participate.

As part of routine care at the Maternal Fetal Care Center, pregnant women that are active smokers are encouraged to quit. If the patient is interested in quitting smoking, the physician or pharmacist will schedule a smoking-cessation consultation visit with maternal-fetal clinical pharmacist. During this pilot study, women who have expressed interest in quitting and meet the inclusion and exclusion criteria will be approached and offered enrollment in the smoking cessation study. Patients who consent will be randomized to either the texting group or control group. For randomization purposes, an equal number of notecards will be made for the two groups. We will use a random number generator to help with patient randomization. These

**Protocol Title:** Smoking Cessation Following Text Message Intervention in Pregnant Women

---

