If available, delivery details will be abstracted from the patient charts and shall include gestational age at delivery, fetal weight, APGAR scores, and umbilical cord gases.

- c) **If the proposed study is a clinical trial where a drug, vaccine, device or other treatment is compared to a placebo group or comparison treatment group, what are the guidelines or endpoints by which early decisions regarding efficacy or lack of efficacy can be made? For example, it may be reasonable to stop enrollment on a study when efficacy has already been clearly demonstrated, to avoid unnecessary enrollments of additional subjects. Alternatively, it may be reasonable to stop enrollment when it is clear that efficacy will never be demonstrated, given the statistical power of the study as designed. Describe the guidelines that are in place to assist in making these determinations, if relevant to the proposed study.**

N/A

- d) **Describe how data analysis will be performed (statistical tests, methods of evaluating data) and indicate the smallest group/unit for which separate reporting will occur. For studies involving a questionnaire, if data and reliability information are available, please describe or provide references. For full board, unfunded studies describe sample size determination and power analysis. If none, please justify.**

Power Calculation

Based on previous experience, we anticipate 30% of patients will stop smoking at 2 weeks and anticipate texting will increase cessation rates by an additional 5%. Using G\*Power, based on a Chi square test, alpha of 0.05, power of 0.8, and medium effect size of 0.5, we estimate needing 52 patients. We anticipate 15% lost to follow-up or drop outs, so we anticipate needing 60 patients for this pilot project.

G\*Power is a free online statistical tool for calculating power in social, behavioral, and biomedical sciences.

Outcomes and Statistical Analysis

Primary Outcome- Smoking cessation rate verified by exhaled carbon monoxide levels (<8ppm) at 2weeks of quit date between texting and control group

Statistical Analysis- Chi-squared or Fischer's Exact Adjusted for confounders: multiregression

**Protocol Title:** Smoking Cessation Following Text Message Intervention in Pregnant Women

---

Statistical Analysis- Chi-squared or Fischer’s Exact Adjusted for confounders: multiregression analysis

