**\*\*\* Subject Population \*\*\***

**8. Subject Population - In the space below, please detail the participants that you are requesting to recruit (include description of each group requested)**

- a) **Expected age range of subjects. (For example ≥ 18 yrs to 90 yrs).**

18-55yrs of age

- b) **Number of evaluable subjects to be accrued at SLU or SLU site (this includes all sites under the direction of the SLU PI).**

100

Exceeding the number listed here is a protocol violation. Prior IRB approval is required if additional participants are to be accrued. If applicable, this number should be consistent with your power analysis described in 3d.

- c) **Number of evaluable subjects to be accrued study wide. \*?HELP?\***

100

- d) **If applicable, state the rationale for involvement of potentially vulnerable subjects to be entered into the study, including minors, pregnant women, economically and educationally disadvantaged, or decisionally impaired individuals. Specify the measures being taken to minimize the risks and the chance of harm to the potentially vulnerable subjects.**

The use of pharmacological aids for smoking cessation is recommended as a potential option by the American College of Obstetrics and Gynecology for pregnant women since they are considered safer than continued smoking during pregnancy. . This study will look at adding text messages to see if cessation rates improve.

**Protocol Title:** Smoking Cessation Following Text Message Intervention in Pregnant Women

---

Since this study is looking at pregnant women who smoke we would be unable to perform this study without the inclusion of pregnant women.

- e) **If women, minorities, or minors are not included, a clear compelling rationale must be provided unless not applicable. Examples for not including minors: disease does not occur in children; drug or device would interfere with normal growth and development; etc. If federally funded reference appropriate section of the sponsors protocol/grant. \*?HELP?\***

Minors are excluded from participation because the standard of care medications are not FDA approved for minors.

- f) **If any specifically targeted subjects are students, employees, or laboratory personnel, specify the measures being taken to minimize the risks and the chance of harm to these potentially vulnerable subjects.**

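### Section 3d claims 80% power with 52 patients, but for its own hypothesis of 30% versus 35% cessation the power is about 7%

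*Combined protocol and SAP*

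**What the plan says.** The Power Calculation in section 3d gives the expected rates: "we anticipate 30% of patients will stop smoking at 2 weeks and anticipate texting will increase cessation rates by an additional 5"%. The next sentence bases the sample size on a chi-square test with "alpha of 0.05, power of 0.8, and medium effect size of 0.5, we estimate needing 52 patients". An allowance of 15% for loss to follow-up raises this to 60 enrolled.

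The primary outcome is carbon-monoxide-verified cessation two weeks after the quit date, compared between the two groups. The named test is "Statistical Analysis- Chi-squared or Fischer"'s exact, with a regression adjustment for confounders. Section 3b plans equal allocation: "For randomization purposes, an equal number of notecards will be made for the two groups".

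Sections 8b and 8c each give 100 evaluable subjects. The form says of that entry: "If applicable, this number should be consistent with your power analysis described in 3d". Item 8c of the Expedited Paragraphs, which is marked, reads "Previously approved research where the remaining research activities are limited to data analysis".

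**The concern.** The two sentences of the power calculation describe different trials. The first expects a gain of five percentage points. The second assumes a standardised effect of 0.5, and nothing in the section links it to the rates just given. If the two do not correspond, the stated power of 0.8 does not apply to the hypothesis.

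The claim matters when the result is read. A reader told that the trial had 80% power may take a non-significant result as evidence that texting does not help. If the true power is close to the type I error rate, a non-significant result is what one expects whether or not texting adds five points.

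**Working it through.** **Inputs.** From section 3d: control rate 30%; gain of 5, read as percentage points, so 35% with texting; alpha 0.05, taken as two-sided; power 0.8; effect size 0.5; 52 patients. From section 3b: equal arms, so 26 per arm. From sections 8b and 8c: 100 evaluable, so 50 per arm. The index behind 0.5 is not named. I take it as w, the index for a chi-square test.

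**1. Reproducing the 52.** Chi-square power comes from the noncentral chi-square distribution with noncentrality N × w². Two groups and a binary outcome give one degree of freedom.
- w = 0.5, 1 df: N = 31 gives 0.795 and N = 32 gives 0.807. The stated inputs therefore require 32, not 52.
- 52 is reached with 5 df at power 0.80 (N = 51 gives 0.797; N = 52 gives 0.806), or with 1 df at power 0.95 (N = 51 gives 0.9464; N = 52 gives 0.9501). The document does not show which of these, if either, was used.
- Reading 0.5 as Cohen's h or d gives 63 per arm two-sided or 50 per arm one-sided, not 52 in total.

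**2. Effect size for the stated rates.** With equal arms, w = (p2 − p1) / (2 × √(p̄(1 − p̄))), where p̄ is the mean of the two rates.
- 30% versus 35%: 0.05 / (2 × √(0.325 × 0.675)) = 0.053. The ratio to 0.5 is 0.5 / 0.0534 = 9.4.
- Solving w = 0.5 with p1 = 0.30 gives p2 = 0.798.

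**3. Power for 30% versus 35%, two-sided 0.05.** This sums over all outcomes of two independent binomials, using the uncorrected chi-square and the two-sided Fisher test. The last two columns give the chance that the observed texting rate is no higher than the control rate, and the 95% CI half-width, 1.96 × √((0.30 × 0.70 + 0.35 × 0.65) / n).

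| Per arm | Chi-square | Fisher | Texting no better than control | CI half-width |
|---|---|---|---|---|
| 26 | 7.3% | 3.7% | 41% | 25 points |
| 30 | 6.7% | 3.9% | 39% | 24 points |
| 50 | 8.2% | 5.5% | 33% | 18 points |

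The noncentral approximation for 52 patients agrees: the noncentrality is 52 × 0.0534² = 0.148, and power is 6.7%.

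**4. Size needed for 80% power.** n per arm = [1.96 × √(2 × 0.325 × 0.675) + 0.8416 × √(0.30 × 0.70 + 0.35 × 0.65)]² / 0.05² = (1.298 + 0.557)² / 0.0025 = 1,376.3, so 1,377 per arm or 2,754 in total.

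**5. What the trial can detect with 80% power from a 30% control rate.**
- 26 per arm: 69% by chi-square, 72% by Fisher.
- 50 per arm: 57% by chi-square, 59% by Fisher.

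If the expected gain were doubled (30% versus 40%), power would be 13% by chi-square and 7% by Fisher with 26 per arm, and 18% and 13% with 50 per arm.

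**6. Sensitivity to the assumptions.**
- Control rates of 20% to 40% with a five-point gain give chi-square power of 6.5% to 9.3% for 26 to 50 per arm.
- A one-sided test with 26 per arm gives about 10%.
- Reading the 5% as relative (30% versus 31.5%) gives at most about 6% with 26 per arm.

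**7. Sample-size bookkeeping.** The 60 is 52 × 1.15 = 59.8. Dividing by the retained fraction gives 52 / 0.85 = 61.2, so 62. Enrolling 60 and losing 15% leaves 60 × 0.85 = 51 evaluable.

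**The case against.** The strongest reply is that the protocol calls this a pilot, and a pilot need not be powered for efficacy. That would be a good reason to make no power claim. It does not support an explicit claim of 0.8, particularly when the primary outcome is tested between groups for efficacy.

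A second reply is that nothing can now be done, because the sample size is settled. That stands as far as recruitment goes and limits the remedy to text and reporting. The interpretation of the result is still open, and that is where the power claim does its harm.

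Third, the plan might point to its background evidence for a large effect. The largest text-message trial it cites reports: "At 6-months abstinence was significantly increased in the intervention group versus the control group (10.7% vs. 4.9"%). In that trial's own terms w is 0.058 / (2 × √(0.078 × 0.922)) = 0.11. It is fair to say that w depends on the base rate, and that six-month abstinence outside pregnancy is not two-week abstinence within it. Carrying that trial's odds ratio (2.33) to a 30% base gives about 50% and w = 0.20; carrying its risk ratio (2.18) gives about 66% and w = 0.36. Both are still below 0.5, so the trial does not supply the assumption. The case does not depend on this comparison.

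Some smaller points also stand. With 52 patients the smallest expected cell is about 26 × 0.325 = 8.5, so under the usual rule of five the chi-square test would apply, but section 3d states no rule. Section 3b places women who decline texts in the standard-of-care group, so the arms may be unequal, which would lower power slightly. The 100 in section 8 also serves as an accrual ceiling, although the form labels it evaluable and asks for consistency with 3d. None of these restores the stated power.

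**Conclusion.** The concern holds and must be fixed. For the effect the plan expects, power is about 7% by chi-square and 4% by Fisher with 52 evaluable patients, and about 8% and 5% with 100. If texting truly adds five points, the chi-square test with 26 per arm would be non-significant about 93% of the time. A significance test at this size therefore says almost nothing about the stated hypothesis. Separately, 52 is not what the stated inputs produce for a two-by-two table, and how it arose cannot be determined.

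These figures assume a two-sided test, equal arms and an absolute gain of five points. The alternatives checked do not bring power anywhere near 80%. Exact power moves irregularly with sample size, so the first digit is all that should be relied on.

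**What to change.** Add no patients. In section 3d:
- Withdraw the claim of 80% power based on effect size 0.5.
- Name the primary test, or the rule for choosing between chi-square and Fisher.
- State the actual power and detectable difference at the size used. For example: with 26 evaluable per arm, power for 30% versus 35% is about 7% (chi-square) or 4% (Fisher); 80% power is reached only near 30% versus 69% (chi-square) or 72% (Fisher).
- Make the primary report the difference in verified cessation rates with its 95% confidence interval.

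Reconcile the 52 and 60 in section 3d with the 100 in sections 8b and 8c, and label each figure as enrolled or evaluable.

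The cost is wording in three places and one reported estimate with its interval. No extra patients, visits or data are needed. The stated power becomes much less favourable.

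### Section 3d: 60 enrolled with the stated 15% loss leaves 51 evaluable, one short of the stated 52 (minor, but wrong as written)

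*Combined protocol and SAP*

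**What the plan says.** Section 3d, under Power Calculation, bases the sample size on G*Power, "based on a Chi square test, alpha of 0.05, power of 0.8, and medium effect size of 0.5". From the "medium effect size of 0.5, we estimate needing 52 patients" it moves to the enrolment figure in one step: "We anticipate 15% lost to follow-up or drop outs, so we anticipate needing 60 patients for this pilot project". The wording makes 60 a consequence of 52 and the 15% loss. No inflation formula is shown, and the degrees of freedom are not given.

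The same paragraph expects 30% of patients to have stopped smoking at 2 weeks and texting to add 5%.

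Sections 8b and 8c of the application give a different figure. The entry for "Number of evaluable subjects to be accrued study wide" is 100, and the entry for the site is also 100. The form says that the accrual number should agree with the power analysis in 3d.

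**The concern.** Patients can be lost only from among those enrolled, so a 15% loss applies to the enrolment figure. The number to enrol is then the evaluable number divided by 0.85. Adding 15% to the evaluable number gives a smaller result and leaves the trial short of its own requirement.

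The primary outcome is cessation verified by exhaled carbon monoxide at 2 weeks. A woman who misses that visit has no verified outcome, and no section counts such women as smokers. On the plan as written, losses therefore reduce the number analysed. What is at stake is whether the enrolment figure in 3d delivers the number that 3d says is needed.

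**Working it through.** **Inputs**, all from section 3d unless noted:
- evaluable number: 52 in total
- loss: 15%
- enrolment: 60 in total
- alpha 0.05, power 0.80, effect size 0.5. The index is not named; Cohen's w is assumed because the test is a chi-square.
- expected quit rates: 30% and 35%, reading the extra 5% as absolute percentage points
- allocation 1:1 (section 3b: "an equal number of notecards will be made for the two groups")

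**1. Reproduce the plan's 60.** 52 x 1.15 = 59.8, which rounds to 60. This matches the stated figure, but the route is inferred.

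**2. What 60 yields.** 60 x (1 - 0.15) = 51.0 evaluable, and 52 - 51 = 1 short. Sixty keeps 52 only if loss is at most 1 - 52/60 = 13.3%.

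**3. What 52 requires.** 52/(1 - 0.15) = 61.18, rounded up to 62. Check: 61 x 0.85 = 51.85, still short; 62 x 0.85 = 52.7, enough. The difference from the plan is 62 - 60 = 2 enrolled.

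**4. Effect on power at w = 0.5.** Power is the probability that a noncentral chi-square variable with noncentrality N x w² exceeds the 5% critical value of the central chi-square. The smallest N for 80% power is:

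| df | 1 | 2 | 3 | 4 | 5 | 6 | 7 |
|---|---|---|---|---|---|---|---|
| N | 32 | 39 | 44 | 48 | 52 | 55 | 58 |

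Of these, only df = 5 reproduces 52. A comparison of two arms on quit or not quit has (2 - 1) x (2 - 1) = 1 degree of freedom.

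| Basis | Power at 52 | Power at 51 |
|---|---|---|
| w = 0.5, df = 5 | 80.6% | 79.7% |
| w = 0.5, df = 1 | 95.0% | 94.6% |

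The lost patient costs 0.9 points on the first basis and 0.4 on the second.

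**5. Effect on power for the plan's own rates.** With equal arms at 30% and 35%, the mean rate is 32.5% and each arm lies 2.5 points from it. So w = sqrt(0.025²/(0.325 x 0.675)) = 0.053, about a tenth of 0.5. On the same method with df = 1, power is 6.7% at 51, 6.7% at 52 and 7.0% at 62. A normal-approximation formula for two proportions gives about 6% at these sizes. Detecting 30% versus 35% with 80% power needs about 1,377 per arm, or 2,754 in total.

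**The case against.** The strongest objection is that this is immaterial. The gap is one patient, the figures are worded as anticipations for a pilot, and 60 is enough if loss stays at or below 13.3%. That stands as to size. It does not make the sentence correct, because the stated loss is 15% and 60 is presented as following from it.

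A second objection is that 60 may not be the operative target. If 100 evaluable subjects are accrued, as sections 8b and 8c state, there is no shortfall; even 100 enrolled with 15% lost would leave 100 x 0.85 = 85. This also stands in part. Nothing in the documents says which figure governs, so 3d still needs correcting, and changing 60 to 62 would leave the conflict with 100 in place.

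A third objection is that 52 is itself doubtful: at w = 0.5 a two-by-two table needs only 32, and the expected rates imply a far smaller effect. That stands, and it limits what this point can claim.

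Three stronger readings are tempting and are not supported:
- **That the plan multiplied by 1.15.** The match with 59.8 makes this likely, but no formula appears. The shortfall holds by whatever route 60 was reached.
- **That this slip leaves the trial underpowered.** It moves power by less than one point on any basis above. The low power for 30% versus 35% comes from the choice of effect size.
- **That 62 would secure 80% power.** It would secure 52 evaluable at 15% loss, and nothing more.

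**Conclusion.** The point holds as a minor arithmetic inconsistency. By the plan's own loss rate, its enrolment figure yields one evaluable patient fewer than it says it needs, and the matching enrolment figure is two higher. This assumes that the 15% applies to those enrolled and that women without a 2-week verified outcome drop out of the analysis; the documents give no rule to the contrary.

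The power figures further assume that 0.5 is Cohen's w, and they depend on the degrees of freedom, which the plan does not state. Correcting the inflation step leaves two larger matters open: the conflict between 60 and 100, and the mismatch between an effect size of 0.5 and a 5-point difference.

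**What to change.** In section 3d, do one of the following:
- keep 60 and state that it yields 51 evaluable at 15% loss, or
- state that 62 enrolled is the figure that yields 52 evaluable at 15% loss.

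In the same edit, reconcile the 3d figure with the 100 evaluable subjects in sections 8b and 8c and say which governs. Then restate power for the evaluable number, naming the effect-size index, its value, the degrees of freedom and the quit rates it represents. If the sample size is rebuilt on another basis, divide the new evaluable number by 0.85.

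The inflation step costs one line and, with the first option, no extra patients; the second option adds two. Reconciling 60 with 100 and restating power takes a short rewrite of the power paragraph and, depending on which figure governs, of the entries in 8b and 8c. No study procedure changes.
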